3 STUDY DESIGN

3.1 General Study Design

This study is an open-label extension study to evaluate the long-term safety and tolerability of pimavanserin in subjects with major depressive disorder and inadequate response to antidepressant treatment. This study will be conducted as a 52-week extension of Studies ACP-103-054, and -059.

Subjects who have completed Studies ACP-103-054, or -059, who continue to meet entry criteria, and who may continue to benefit from adjunctive pimavanserin treatment based on the Investigator's judgment will be included in this long-term extension study.

[figure not shown]
All subjects will receive pimavanserin once-daily dosing at 34 mg over 52 weeks of treatment. During the treatment period, clinic visits will be conducted at Baseline and Weeks 2, 4, 8, 12, 16, 28, 40, and 52 (EOT), or upon early termination (ET) from the study.

Study drug will be dispensed to the subject to take home at the Baseline visit and at Weeks 4, 8, 12, 16, 28, and 40. The subject will be instructed to take the first dose of study drug on the day after the Baseline visit. It is recommended that the subject should take the study drug at approximately the same time each day.

A 30-day safety follow-up telephone contact is to be completed for subjects who complete the treatment period of the study, as well as those who discontinue prematurely from the study.

Figure 1 illustrates the study design.

Figure 1 Schematic of Study Design

Abbreviation: QD=once daily

Note: The antecedent study is either Study ACP-103-054 or Study ACP-103-059.

3.2 Schedule of Assessments

Schedule of events and assessments can be found in [Appendix A](#).

3.3 Randomization

Not applicable.

3.4 Blinding

Not applicable.

3.5 Determination of Sample Size

It is estimated that approximately 420 subjects from Study ACP-103-054 and Study ACP-103-059 will be eligible to enter this study. The sample size for this study is not based on statistical power, but will depend on the number of subjects who transition into this open-label extension study from the antecedent studies, Study ACP-103-054 and Study ACP-103-059.

ACP-103-054, -059 and -055 were stopped early; the estimated number of subjects will be less than originally estimated.

3.6 Coronavirus Disease 2019

In March, 2020, the emerging coronavirus disease 2019 (COVID-19) pandemic resulted in implementation of urgent safety measures designed to ensure subject safety. Mechanisms to record information on the potential impact of the COVID-19 pandemic on data itself, as well as data collection and integrity, were implemented (as detailed in the “Guidance for Site Documentation and Data Management Querying of Data Impacted by COVID-19” [GSD] in the Data Management Plan).

Screening and enrollment into studies ACP-103-054 and ACP-103-059 were closed and enrollment into ACP-103-055 was allowed to continue. The impact of COVID-19 on the statistical analysis is discussed in each of the relevant sections of this SAP.

Subjects who remained in this study who could not attend clinic visits were allowed to participate in remote visits via telephone or video, or site staff conducted the visit in a subject’s home. Sites were required to document details of all visits that are administered remotely.

Afterwards, ACP-103-055 was stopped early and the remaining subjects were discontinued in the study.

4 ANALYSIS SETS

The Safety Analysis Set will consist of all enrolled subjects who have taken at least one dose of open-label study drug. The Safety Analysis Set will be used for all analyses.

5 DATA HANDLING CONVENTIONS

All data collected in the study will be listed.

5.1 General Data Reporting Conventions

For continuous variables, the following summary statistics will be provided: number of subjects, mean, standard error of the mean (SE), standard deviation (SD), minimum, maximum, and median. Unless specified otherwise, means, and medians will be presented to one more decimal place than the raw data, and the SDs and SEs will be presented to 2 more decimal places than the raw data.

For categorical variables, summaries will include the number and percentage of subjects in each category, using the number of subjects with non-missing values as the denominator for the percentages (unless otherwise specified). Categories with zero counts will not have zero percentages displayed. Percentages will be presented to 1 decimal place.

When converting number of days to months, it will be calculated as the number of days divided by 365.25 and then multiplied by 12. When converting number of days to years, it will be calculated as the number of days divided by 365.25.

No hypothesis testing is planned. Descriptive summaries of all safety and efficacy endpoints will be provided.

All safety and efficacy endpoints will be summarized for the Safety Analysis Set. In addition, summaries by treatment group according to the original double-blinded treatment actually received in the antecedent study (placebo or pimavanserin) will also be provided.

For each continuous measure in safety and efficacy analyses, change from Baseline results will be presented in two ways:

1. Main analysis: using the Baseline from Study ACP-103-055 and reporting the changes across Study ACP-103-055 timepoints
2. Exploratory analysis: using the Baseline from the antecedent study (ACP-103-054 or ACP-103-059), and reporting the changes across Study ACP-103-055 timepoints

For the treatment responder rate, the summary will also be presented in two ways:

1. Main analysis: using the Baseline from Study ACP-103-055 and reporting the rate across Study ACP-103-055 timepoints
2. Exploratory analysis: using the Baseline from the antecedent study (ACP-103-054 or ACP-103-059), and reporting the rate across Study ACP-103-055 timepoints

The treatment remission rate and the percentage of subjects with sexual dysfunction will also be summarized across Study ACP-103-055 timepoints using the Baseline from Study ACP-103-055 and the Baseline from the antecedent double-blind studies as reference points.

5.2 Derived Variables

In general, the assessment scale total scores and subscores will be derived within the analysis datasets. In the event that total scores and/or subscores are also collected on the electronic case report form (eCRF), the derived values will be used for all analyses. Both the raw and derived scores will be presented in listings.

5.2.1 Columbia-Suicide Severity Rating Scale (C-SSRS)

The C-SSRS is assessed at Baseline, Weeks 2, 4, 8, 12, 16, 28, 40, and 52 (EOT/ET). C-SSRS is a safety assessment and subjects rolled over from all antecedent studies will be assessed.

The C-SSRS version assessing information since the last visit will be completed at all visits (including the Baseline visit).

There are 5 questions about suicidal ideation, representing 5 types of suicidal ideation: wish to be dead; non-specific active suicidal thoughts; active suicidal ideation with any methods (not plan) without intent to act; active suicidal ideation with some intent to act, without specific plan; active suicidal ideation with specific plan and intent. If a subject answers “yes” to any of these 5 questions, this subject will be counted as having suicidal ideation.

There are 5 questions about suicidal behavior, representing 5 types of suicidal behavior: preparatory acts or behavior; aborted attempt; interrupted attempt; actual attempt; suicide. If a subject answers “yes” to any of these 5 questions, this subject will be counted as having suicidal behavior.

Suicidality is defined as a subject who reported at least 1 occurrence of suicidal ideation or at least 1 occurrence of suicidal behavior at any post-Baseline visit including unscheduled and out of window visits.

Missing C-SSRS item scores will not be imputed.

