### **6.3.5 Columbia–Suicide Severity Rating Scale**

The C-SSRS monitors changes in suicidal thinking and behavior over time, in order to determine risk ([Posner et al. 2011](#)). The following four constructs are measured: the severity of ideation, the intensity of ideation, behavior, and lethality.

For subjects who completed the Baseline/Screening version in Study ACP-103-054 or Study ACP-103-059, the Since Last Visit version will be administered at all visits. The C-SSRS results for each subject should be reviewed by the Investigator at each visit. If at any time the C-SSRS results for a given subject reveal potential suicidality, then the Investigator should assess the clinical significance of such results. If a clinically significant risk of suicidality is identified for a subject, then the Investigator should discontinue the subject and implement appropriate treatment ([Section 4.4](#)).

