14.6 Other Safety Variables

14.6.1 Suicidality Based on C-SSRS

The event counts and the number and percentage of subjects reporting any post double-blind Baseline suicidal ideation, suicidal behavior, or suicidality will be tabulated by the double-blind treatment group in the antecedent studies across the timepoints of both the antecedent study and the open-label Study ACP-103-055. The event counts and the number and percentage of subjects reporting any post-Baseline non-suicidal self-injurious behavior will also be tabulated. For calculating the percentages, the denominator will be the number of subjects in the Safety Analysis Set. In addition, a summary counting of any reports post open-label Baseline will be presented.

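### Suicidality is counted from C-SSRS forms alone but divided by every treated subject, so an event with no form to record it may count as no event.

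*SAP*

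**What the plan says.** **Numerator.** SAP 5.2.1 defines suicidality as "a subject who reported at least 1 occurrence of suicidal ideation or at least 1 occurrence of suicidal behavior at any post-Baseline visit". Ideation and behavior are each built from a yes answer to one of five C-SSRS questions. The behavior questions cover "preparatory acts or behavior; aborted attempt; interrupted attempt; actual attempt; suicide". Forms count "at any post-Baseline visit including unscheduled and out of window visits". The same section adds: "Missing C-SSRS item scores will not be imputed". Neither 5.2.1 nor 14.6.1 draws on adverse event, serious adverse event or death records.

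**Denominator.** SAP 14.6.1 states: "For calculating the percentages, the denominator will be the number of subjects in the Safety Analysis Set". SAP 4 defines that set as "all enrolled subjects who have taken at least one dose of open-label study drug", so no C-SSRS after Baseline is needed to be in it.

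**Tables.** The main table in 14.6.1 runs across the antecedent study and this one. A further summary counts reports after the open-label Baseline.

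**Timing.** The C-SSRS is scheduled from Baseline to Week 52 (EOT/ET) and at unscheduled visits. The schedule (Protocol Table S-1, SAP Appendix A) has no C-SSRS mark at the Week 56 call. Protocol 6.4 lists only concomitant medication and adverse events for that contact. SAP 14.1 counts an adverse event as treatment-emergent up to 30 days after the last open-label dose.

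**The concern.** The numerator needs a completed form and the denominator does not. A treated subject who was never assessed, or whose event came after the last assessment, enters the percentage as a subject without suicidality, not as one with missing information.

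Elsewhere the SAP handles this differently. Its default in 5.1 is to divide by subjects with non-missing values. Its overall post-Baseline summaries of potentially clinically important laboratory, vital sign and ECG values (14.2, 14.3, 14.4) divide by subjects with at least one post-Baseline value.

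Suicidality is the first-listed exploratory safety topic, in a population with major depressive disorder. If a suicide or attempt is known only from an adverse event or death record, the suicidality table could show fewer suicidal events than the serious or fatal event tables of the same report, and no planned output would explain the difference.

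**Working it through.** The plan states no rate, power or precision figure on this point, so there is nothing to reproduce. The check covers the counting rule, the schedule, and the size per case.

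**1. Counting rule.** Let N be the Safety Analysis Set, k the subjects with an event recorded on a form, and m the subjects with an event but no form recording it.
- Reported percentage: k / N.
- Percentage if all known events counted: (k + m) / N.
- Shortfall: m / N. Each missed subject adds 0 to the numerator and 1 to the denominator.

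**2. Schedule.** Take a subject who completes the Week 52 or early-termination C-SSRS and makes an attempt within 30 days of the last dose.
- SAP 14.1: the attempt is a treatment-emergent adverse event.
- Protocol 6.4: the follow-up call asks about adverse events, so it can be recorded there.
- Table S-1: no C-SSRS is scheduled at that call. Only an unscheduled visit with a C-SSRS would bring the attempt into the suicidality count.

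This gap needs no loss to follow-up; it is open to completers and early terminators alike.

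**3. Size per missed subject (m = 1).** The planned N is about 420 (Protocol 9.3, SAP 3.5). SAP 3.5 says the actual number will be lower and does not give it, so the smaller values are assumptions.

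| N | Shortfall, 1/N |
|---|---|
| 420 (planned) | 0.24 points |
| 300 (assumed) | 0.33 points |
| 200 (assumed) | 0.50 points |
| 100 (assumed) | 1.00 point |

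**4. Size as a share of cases.** If the true percentage is p and a share u of true cases has no form recording the event, the table shows p × (1 − u). Both p and u are assumed.

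| p | u = 2% | u = 5% | u = 10% |
|---|---|---|---|
| 5% | 4.90% | 4.75% | 4.50% |
| 10% | 9.80% | 9.50% | 9.00% |

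**5. What a different denominator repairs.** Assume N = 200, of whom 190 have a post-Baseline form, and a true percentage of 10% in both the assessed and the unassessed. There are 20 true cases, of which 19 are counted. Then 19/200 = 9.5% and 19/190 = 10.0%. Dividing by those assessed restores the percentage only if the unassessed carry the same risk. It does nothing for an event after a subject's last form, because that subject is already among the assessed. Both additions in the fix are therefore needed.

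**The case against.** **Stronger readings that the documents do not support.** A reader might infer that a completed suicide is always scored as no suicidality. It is not: suicide is one of the five counted behaviors and unscheduled visits count, so a form completed after a death would register. The documents neither require nor rule out such a form, and the result is open. A reader might also infer that such events vanish from the report. They do not: SAP 14.1 tabulates treatment-emergent, serious and fatal events by preferred term, and lists serious events and deaths separately. Nor can any fixed fraction of cases be claimed missing, because no rates are given.

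**Capture routes for attempts.** There are several:
- Protocol 7.4.2 has subjects with a serious event seen as soon as feasible.
- Protocol 6.5 includes the C-SSRS among the assessments generally recorded at unscheduled visits.
- Protocol 4.3 and 4.4.1 ask for every reasonable effort to obtain the early-termination evaluations, which include the C-SSRS.
- Protocol 6.3.8.1 makes the C-SSRS a priority at remote visits.

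Protocol 6.3.5 says "If a clinically significant risk of suicidality is identified for a subject, then the Investigator should discontinue the subject and implement appropriate treatment". That ends the regular visits but also prompts the early-termination C-SSRS, so it does not by itself show that attempts are missed selectively.

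**Scope.** The endpoint in Protocol 2.2.1 is the C-SSRS, and SAP 14.6.1 is headed as based on it. Adding adverse-event cases to the main count would create a composite that the protocol did not name.

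**What stands.** These points narrow the claim but leave the gap. The capture routes are efforts rather than guarantees, and none of them schedules a C-SSRS at the Week 56 contact. The heading discloses the source of the data, but not that unassessed subjects count as event-free. Nothing in the SAP reconciles the suicidality table with the adverse event tables. The scope argument is a reason to keep the C-SSRS rows intact and show the other source beside them.

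**Conclusion.** The concern holds in this form. The suicidality percentages rest on C-SSRS forms alone, over a denominator that includes subjects with no form after open-label Baseline and subjects whose event follows their last form. A suicide or attempt known only from adverse event or death records may be left out of the suicidality table while appearing in the adverse event, serious event or fatal event tables.

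The size is unknown. Per missed subject it is 0.24 percentage points at the planned N of 420 and 0.50 at an assumed N of 200. This is small in a descriptive, exploratory analysis with no testing, but the cases concerned would be among the most serious in the study.

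Two assumptions matter. First, the denominator sentence in 14.6.1 comes before the sentence that adds the open-label summary; I read it as covering both, since no other denominator is named there. Second, no form is assumed to exist for the missed cases. If sites complete a C-SSRS after every death and every late attempt, the second gap closes.

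This is an inexpensive improvement that should be made. It does not undermine the study's primary analysis.

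**What to change.** Amend SAP 5.2.1 and 14.6.1 as follows.

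1. Keep the C-SSRS-based rows unchanged as the protocol endpoint.
2. In the summary after open-label Baseline, add two rows: *AE/death record only* and *either source*. Use a fixed list of MedDRA terms for suicide, suicide attempt and suicidal ideation, with onset from the open-label first dose to the open-label last dose plus 30 days, matching SAP 14.1.
3. Report the number of subjects with at least one C-SSRS after open-label Baseline, and give the C-SSRS percentages on that number beside those on the full Safety Analysis Set.
4. State how a completed suicide enters the table when no C-SSRS form exists for it.

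**Cost.** One term list, one derived flag and a little programming, all on data already collected in this study. Some adverse event terms may not separate an attempt from non-suicidal self-injury, which is why cases known only from those records get their own row. Extending the rows to the table that spans the double-blind period would need the antecedent studies' adverse event and death data; that step is optional.

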## 4.2 Exclusion Criteria

A subject must meet none of the following exclusion criteria to be eligible for the study.

1. Is judged by the Investigator or the Medical Monitor to be inappropriate for the study, due to AEs, medical condition, or noncompliance with investigational product or study procedures in Study ACP-103-054 or Study ACP-103-059, or is judged to be a danger to self or others
2. Has any of the following electrocardiogram (ECG) results at Baseline (i.e., Week 6/ EOT visit of Study ACP-103-054 or Study ACP-103-059):
  - a. If the subject is **not** on citalopram, escitalopram, or venlafaxine (immediate or extended release):
    - i. QTcF >450 ms, if QRS duration <120 ms
    - ii. QTcF >470 ms, if QRS duration  $\geq$ 120 ms
  - b. If the subject is on citalopram, escitalopram, or venlafaxine (immediate or extended release):
    - i. QTcF >425 ms, if QRS duration <120 ms
    - ii. QTcF >450 ms, if QRS duration  $\geq$ 120 ms
3. Has a heart rate (as measured by peripheral pulse rate) <50 beats per minute at Baseline (i.e., the Week 6/EOT visit of Study ACP-103-054 or Study ACP-103-059) not explained by regular exercise or medication, in discussion with the Medical Monitor

4. Has a body mass index (BMI)  $<18.5 \text{ kg/m}^2$  or known unintentional clinically significant weight change (i.e.,  $\pm \geq 7\%$  of body weight) in Study ACP-103-054 or Study ACP-103-059 as assessed by the Investigator
5. Has clinically significant laboratory abnormalities that, in the judgment of the Investigator or Medical Monitor, would either:
  - a. jeopardize the safe participation of the subject in the study; OR
  - b. would interfere with the conduct or interpretation of safety or efficacy evaluations in the study
6. Is suicidal as defined below at Visit 1 (Baseline) of the present study:
  - a. An answer of “yes” to C-SSRS questions 4 or 5 (current or over the last 6 months); OR
  - b. Has attempted suicide within 1 year prior to Visit 1 (Baseline); OR
  - c. Is actively suicidal in the Investigator’s judgment
7. Has developed delirium or a neurologic, cardiovascular, respiratory, gastrointestinal, renal, hepatic, hematologic, or other medical or mental disorder, including cancer or malignancies that, in the judgment of the Investigator or the Medical Monitor, would increase the risk associated with taking study medication or significantly interfere with the conduct or interpretation of the study

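### The C-SSRS summary tables show neither the ideation level nor a comparison with the subject's Baseline status, so persisting passive ideation cannot be told from new or worsened ideation

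*SAP*

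**What the plan says.** SAP 5.2.1 describes five ideation questions, "representing 5 types of suicidal ideation: wish to be dead; non-specific active suicidal thoughts" and upward to active ideation with a plan and intent. A yes "to any of these 5 questions, this subject will be counted as having suicidal ideation". Five behavior questions are treated in the same way. Suicidality is then "at least 1 occurrence of suicidal ideation or at least 1 occurrence of suicidal behavior at any post-Baseline visit", with unscheduled and out-of-window visits included.

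The form used is the same throughout: "The C-SSRS version assessing information since the last visit will be completed at all visits (including the Baseline visit").

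SAP 14.6.1 plans two summaries. The first counts both events and people, with percentages: those "reporting any post double-blind Baseline suicidal ideation, suicidal behavior, or suicidality will be tabulated by the double-blind treatment group", over the visits of both the antecedent and the open-label study. For the second: "In addition, a summary counting of any reports post open-label Baseline will be presented". Non-suicidal self-injury is also tabulated. The denominator is the whole Safety Analysis Set.

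Protocol 6.3.5 describes the instrument's purpose: "The C-SSRS monitors changes in suicidal thinking and behavior over time". It lists severity and intensity of ideation among the constructs measured. Protocol 4.2, exclusion 6a, removes subjects who answer yes to "C-SSRS questions 4 or 5 (current or over the last 6 months"). Exclusions 6b, 6c and 1 also remove those with an attempt in the past year, those the investigator judges actively suicidal, and those judged a danger to themselves or others.

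**The concern.** Suicidality is the first exploratory safety objective listed in Protocol 2.2. The useful questions are whether ideation appeared in subjects who had none, and whether it rose in those who had some. A table of any positive report answers neither. A subject who reports a passive wish to be dead at Baseline and again at Week 2 is counted exactly like one who goes from nothing to a plan with intent. A subject who moves from type 1 to type 5 looks the same as one who stays at type 1.

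The loss matters more here because every subject receives pimavanserin. With no concurrent control, each subject's own Baseline is the main reference available for separating background from emergence. The SAP uses that reference elsewhere: laboratory values (14.2) and the cardiologist's ECG interpretations (14.4) both get shift tables from Baseline. The C-SSRS does not.

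**Working it through.** The plan states no figure for the C-SSRS, and the sample size is not based on power, so there is nothing to reproduce. The check has three parts.

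**1. Is Baseline status used anywhere as a comparator?**
- SAP 5.1 sets out analyses from two Baselines for continuous measures, response, remission and sexual dysfunction. The C-SSRS is not among them.
- SAP 14 repeats the two-Baseline rule for laboratory values, vital signs and ECG only.
- SAP 14.6.1 uses the two Baselines as starting points for counting.
- Under Protocol 3.1 the antecedent end-of-treatment visit is the open-label Baseline visit. A positive report there can therefore enter the first table as an event, but no later report is compared with it.

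**2. Which patterns does the counting rule merge?** Code ideation as 0 (none) or types 1 to 5. Exclusion 6a limits Baseline to 0–3. The worst post-Baseline value can be 0–5.

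- All pairs: 4 × 6 = 24.
- Pairs counted as ideation (post-Baseline value above 0): 4 × 5 = 20.

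| Pattern within the 20 | Pairs |
|---|---|
| Unchanged (1→1, 2→2, 3→3) | 3 |
| Improved but still present (2→1, 3→1, 3→2) | 3 |
| New onset (0→1 to 0→5) | 5 |
| Worsened from existing ideation (4 from type 1, 3 from type 2, 2 from type 3) | 9 |

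New or worsened patterns number 5 + 9 = 14. Patterns with no worsening number 3 + 3 = 6. Patterns reaching type 4 or 5 number 4 × 2 = 8, and all 8 are new or worse because those types are barred at entry. A type 4–5 row would therefore contain no carried-over ideation among eligible subjects. These are counts of patterns, not probabilities.

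**3. What would the table look like?** The documents give no ideation rates, so the rates below are assumptions. The planned number of 420 is used only for scale; SAP 3.5 says the actual number will be lower.

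- If 5%, 15% or 30% have type 1–3 ideation at Baseline that is reported again, the table shows 420 × 0.05 = 21, 420 × 0.15 = 63 or 420 × 0.30 = 126 subjects.
- Suppose that 0.5%, 1% or 3% of all subjects, drawn from that same group, progress to type 4 or 5: 420 × 0.005 ≈ 2, 420 × 0.01 ≈ 4 or 420 × 0.03 ≈ 13.
- The planned table still shows 21, 63 or 126. A new-or-worsened count would move from 0 to 2, 4 or 13.

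The counts shrink in proportion with a smaller sample. The inability to separate the two situations does not.

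**The case against.** The case for leaving the plan alone has real content.

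- **The information is not lost.** SAP 5 lists all collected data, and SAP 5.2 lists raw and derived scores. Behavior is tabulated apart from ideation. Under Protocol 6.3.5 the investigator reviews the C-SSRS at each visit. Worsening may also appear among adverse events (SAP 14.1) or reasons for discontinuation (SAP 6). A reader might infer that worsening is invisible. The documents do not support that: only the ideation level within the summary tables is lost. With fewer subjects than planned, reading listings for rare type 4–5 cases is also more practical.
- **Baseline is not ignored.** A reader might infer that the open-label Baseline result enters no summary. It can enter the first table; it is simply never a comparator.
- **Nothing shows that carried-over ideation dominates.** A reader might infer that the percentage mostly reflects ideation present at entry. The documents give no rate from which to judge this, and exclusions 1, 6b and 6c narrow entry further.
- **The SAP does not contradict the protocol.** Protocol 9.5.2 promises only the number and percentage with ideation or behavior, and the SAP delivers that. The sentence on monitoring change describes the instrument and is not an analysis commitment. The endpoint is exploratory and descriptive.
- **Table specifications are in a separate document (SAP 1).** A breakdown there cannot be excluded, but neither the SAP nor the protocol requires one.
- **A shift table has its own bias.** The Baseline form looks back only to the previous visit of a 6-week study. The worst post-Baseline value is taken over up to 8 visits and 52 weeks, with 12 weeks between the later visits. That favors apparent worsening.

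These points limit the claim and require a footnote on the shift table. They do not supply a prespecified summary of level or change, and readers should not have to build one by hand from listings.

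**Conclusion.** The point holds for the summary tables. As specified, they cannot distinguish persisting passive ideation from new or worsened ideation, including progression to intent or plan. That follows from the counting rule and exclusion 6a alone: 20 of 24 possible patterns share one cell, 6 of them without worsening and 8 at types 4–5. The number of subjects affected cannot be stated, because it depends on ideation rates that the documents do not give and on a sample that will be smaller than 420. The primary endpoint is untouched. This is an inexpensive improvement to an exploratory safety summary, worth making because the study has no control group and the data already exist. It is not an error that undermines the study.

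**What to change.** In SAP 14.6.1, for the open-label period, add:

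- (a) number and percentage of subjects by maximum post-Baseline ideation type, with a combined type 4–5 row, and rows for each behavior type;
- (b) a shift table of worst post-Baseline category (none, ideation 1–3, ideation 4–5, behavior) against open-label Baseline category;
- (c) counts of new onset (none at Baseline) and of worsening (higher than at Baseline).

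Footnote (b) and (c) to say that the Baseline look-back is much shorter than the post-Baseline period, so a shift to the worst value tends toward apparent worsening. The change will not make up for the missing control group.

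The cost is SAP wording and one or two tables. The C-SSRS is already completed at Baseline and at every treatment-period visit, so no procedure or visit changes.
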